6.1.3. General Considerations for Analyses During Maintenance Period

Maintenance Period starts at the first injection of study treatment at Week 16 and ends on the date of Week 52 or the ETV (between Weeks 16 and 52) unless specified otherwise.

For the efficacy and health outcome analyses, baseline is defined as the last available value before the first injection in Induction Period and, in most cases, will be the value recorded at Baseline Visit (Day 1).

Unless otherwise specified, efficacy and health outcome scores at Week 16 prior to entering Maintenance Period will be presented for the visit wise reports for Maintenance Period.

Unless specified otherwise, for the safety analyses during Maintenance Period, baseline is defined as the last available value before first injection in Maintenance Period. In most cases, this will be the measure recorded at Week 16. For TEAEs, baseline is the events ongoing just prior to the first injection of the study drug injection at Week 16.

For patients in the Modified Maintenance Primary Population, Modified Maintenance Secondary Population, Maintenance Primary Population, and Maintenance Secondary Population who met escape criteria (EASI-50 nonresponse) and escaped to lebrikizumab 250 mg Q2W at Weeks 24, 32, 40 and 48, only data in the Maintenance Blinded Period (up to the time of escape) will be included in both efficacy and safety analyses.

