6.1.1. Analysis Populations

Analysis populations are defined in [Table KGAC.6.1](#) along with the analysis they will be used to conduct. [Table KGAC.6.2](#) describes the treatment groups and the comparisons for each study period and the analysis population.

[Figure KGAC.6.1](#) shows a pictorial description of analysis populations.

[figure not shown]

Figure KGAC.6.1. Study periods and analysis populations.

Table KGAC.6.1. Analysis Populations

Population	Description
All Entered Patients	All patients who signed informed consent. Patient flow will be summarized.
Intent-to-Treat (ITT) Population	All randomized patients, even if the patient does not take the assigned treatment, does not receive the correct treatment, or otherwise does not follow the protocol. Patients will be analyzed according to the treatment to which they were assigned.
Modified ITT (mITT) Population	ITT Population excluding all patients from Site 5042. Patients will be analyzed according to the treatment to which they were assigned. Unless otherwise specified, efficacy and health outcomes analyses for the Induction period will be conducted on this population.
Safety Population	All randomized patients who received at least 1 dose of study treatment during Induction Period.
Modified Safety Population	Safety Population excluding all patients from Site 5042. Safety analyses for Induction period will be conducted on this population.
Maintenance Primary Population (MPP)	All patients who were randomized to Lebrikizumab 250 mg Q2W at Baseline Visit and re-randomized to Lebrikizumab 250 mg Q2W, Lebrikizumab 250 mg Q4W or placebo at Week 16 and received at least 1 dose of study treatment during the maintenance period. Patients will be analyzed according to the treatment to which they were re-randomized. Only information prior to escape will be presented.
Modified Maintenance Primary Population (mMPP)	MPP Population excluding all patients from Site 5042. Patients will be analyzed according to the treatment to which they were re-randomized. Only information prior to escape will be presented. Efficacy, health outcomes, and safety analyses for the maintenance period will be conducted on the Modified Maintenance Primary Population

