6.1.3.1. Modified Maintenance Primary and Maintenance Primary Populations

Unless otherwise specified, treatment comparisons of categorical efficacy and health outcomes variables will be analyzed using CMH test with treatment group and covariates as mentioned in Section 6.3 in the model. The CMH p-value will be reported, and the CMH adjusted odds ratio along with the 95% two-sided asymptotic (ie, not continuity corrected) CIs.

Each continuous efficacy and health outcomes measure score, change from baseline and percent improvement from baseline will be summarized by treatment group at all scheduled visits during Maintenance Period including Week 52, using descriptive statistics (n, mean, standard deviation (SD), median, minimum and maximum).

Treatment comparisons for continuous efficacy and health outcome variables will be made using ANCOVA model as specified.

When the ANCOVA is used, the model will include treatment, baseline value and covariates as mentioned in Section 6.3. The ANCOVA analysis will be conducted as described in Section 6.1.2.

The KM product limit method will be used to estimate the survival for time to event analyses (eg, time to loss of IGA response or time to loss of EASI-50 or time to loss of EASI-75). The stratified log-rank test will be performed with treatment group and covariates as mentioned in Section 6.3 in the model. A KM plot of the time to event by treatment group may be provided.

Unless specified otherwise, Fisher's exact test will be used for AEs and other categorical safety measures. Odds ratios will be created with lebrikizumab treatment as the numerator and placebo as the denominator. Continuous vital sign and laboratory values will be analyzed by an ANCOVA model with treatment and baseline value as independent variables.

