6.7. Patient Disposition

The following patient disposition summaries will be provided (details of the analysis populations can be found in Section 6.1.1):

- Total number and percentage of patients entering each statistical analyses population defined in Section 6.1.1.
- The number and percentage of patients who entered the study, failed screening, were randomized at Baseline Visit (Day 1), completed Week 16, completed Week 52, completed the safety Follow-Up Visit and entered long-term extension study. Summary will be provided by the initial randomized treatment group (Analysis population: modified intent-to-treat [mITT]; intent-to-treat [ITT]).
- The number and percentage of patients who completed the study, and the number and percentage of patients who discontinued the study at any time, by the initial randomized treatment group and primary reason for discontinuation (Analysis population: mITT; ITT).
- The number and percentage of patients who completed Induction Period and the number and percentage of patients who discontinued from Induction Period, by treatment group and primary reason for discontinuation (Analysis population: mITT; ITT).

- The number and percentage of patients who completed Maintenance Period and the number and percentage of patients who discontinued from Maintenance Period, by treatment group and primary reason for discontinuation (Analysis populations: Modified Maintenance Primary Population [mMPP]; Modified Maintenance Safety Population [mMSP], Maintenance Primary Population [MPP] and Maintenance Secondary Population [MSP]), in addition, the number and percentage of patients who entered the escape arm will be summarized.

All patients who were randomized (ie, in the ITT population) and discontinued from study treatment during any period from the study will be listed together with the discontinuation reason, and the timing of discontinuation from the study will be reported.

Patient allocation by region, country, and center/site will be summarized with number of patients who entered the study, number of ITT patients for each treatment group, number of patients discontinued from study treatment, and number of patients discontinued from the study.

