6.14.1. Extent of Exposure

Duration of exposure to study treatment will be summarized by treatment group. Drug interruption time period due to the use of systemic rescue therapies will not be removed from study drug exposure calculations as described in compound level safety standards.

The duration of exposure will be calculated as:

Duration of exposure (days)

$$= \text{Date of last visit (scheduled or unscheduled) in the specified Treatment Period} \\ - \text{Date of first dose in Treatment Period} + 1$$

The number and percentage of patients in each of the following categories will be included in the summaries:

- $>0, \geq 7, \geq 14, \geq 30, \geq 60, \geq 90, \geq 112, \geq 120$ days for Induction Period (for Maintenance Period, use $\geq 30, \geq 60, \geq 90, \geq 120, \geq 150, \geq 180, \geq 210, \geq 240$, and ≥ 252 days). Note that patients may be included in more than 1 category.
- >0 to $<7, \geq 7$ to $<14, \geq 14$ to $<30, \geq 30$ to $<60, \geq 60$ to $<90, \geq 90$ to $<120, \geq 120$ days (for Maintenance Period, use >0 to $<30, \geq 30$ to $<60, \geq 60$ to $<90, \geq 90$ to $<120, \geq 120$ to $<150, \geq 150$ to $<180, \geq 180$ to $<210, \geq 210$ to $<240, \geq 240$ to $<252, \geq 252$).

Additional exposure ranges may be considered if necessary. No p-values will be reported.

The summaries will also include the following information:

- Total exposure in patient years, calculated as:

Total exposure in patient years

$$= \frac{\text{Sum of duration of exposures for all patients in treatment group}}{365.25}$$

- Mean and median total dose. Total dose (in mg) is calculated by the number of active injections taken during the treatment period multiplied by dose. For patients in Safety Population randomized to lebrikizumab 250 mg Q2W or patients in Maintenance Primary Population re-randomized to lebrikizumab 250 mg Q2W or Q4W, the total dose (in mg) taken during Induction Period or Maintenance Period will be calculated as follows: *Total lebrikizumab dose = Total number of active injections (including loading doses, if any) received in Induction Period or Maintenance Period × 250.*
- Total number of injections received will be derived based on the *Study Drug Administration* eCRF page and the response to the question “Did you or a caregiver successfully inject the study drug?” on the *Dosing Diary* eCRF page.

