6.14.2. Adverse Events

A TEAE is defined as an event that first occurred or worsened in severity after baseline. The MedDRA Lowest Level Term (LLT) will be used in the treatment-emergent computation. The maximum severity for each LLT during the baseline period will be used as baseline. The treatment period will be included as postbaseline for the analysis. For events with a missing severity during the baseline period, it will be treated as 'mild' in severity for determining treatment-emergence. Events with a missing severity during the postbaseline period will be treated as 'severe' and treatment-emergence will be determined by comparing to baseline severity. For events occurring on the day of first taking study medication, it will be assumed to be posttreatment.

The planned summaries for adverse events are provided in [Table KGAC.6.13](#), and are described more fully in compound level safety standards and in the adverse event-related PhUSE white paper [Analysis and Displays Associated with Adverse Events: Focus on Adverse Events in Phase 2-4 Clinical Trials and Integrated Summary Document (PhUSE 2017)].

Summary tables as described in [Table KGAC.6.13](#) will be presented for the following periods/analysis populations as indicated. Summary tables will include the number and percentage of patients reporting an event. For events that are gender-specific (as defined by MedDRA), the number of participants at risk will include only patients from the given gender.

- Induction Period (Modified Safety Population, mS)
- Induction Period (Safety Population, S) as a sensitivity analysis
- Maintenance Blinded Period (Modified Maintenance Primary Population, mM)
- Maintenance Blinded Period (Maintenance Primary Population, M) as a sensitivity analysis
- Combined Induction Period and Maintenance Period, Combined Induction and Maintenance Periods Plus Follow-Up Period [selective analysis] (All Lebrikizumab Modified Safety Population, mA)
- Combined Induction Period and Maintenance Period, Combined Induction and Maintenance Periods Plus Follow-Up Period [selective analysis] (All Lebrikizumab Safety Population, A) as a sensitivity analysis

Table KGAC.6.13. Summary Tables/Listing Related to Adverse Events

Analysis	Population (Section 6.1.1)
Overview of AEs	mS, S, mM, M, mA, A
Summary of TEAE by PTs	mS, mM
Summary of TEAE by PTs occurring in $\geq 1\%$ of patients	mS, mM
Summary of TEAE by PTs within SOC	mS, mM, mA

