Summary of TEAE PTs by maximum severity	mS, S, mM, M
Summary of SAE by PT within SOC	mS, mM, mA
Summary of AEs leading to treatment discontinuation by PT with SOC	mS, mM, mA
Summary of TEAEs possibly related to study drug by PTs within SOC	mS, mM
Listing of SAEs (including Death)	ITT
Listing of primary AEs leading to study treatment discontinuation	ITT
Listing of TEAEs (for Japan submission only)	S
Listing of TEAEs occurred in safety population but not in modified safety population	

Abbreviations: A = All Lebrikizumab Safety Population; AE = adverse event; ITT = Intent-to-Treat; M = Maintenance Primary Population; mA = Modified All Lebrikizumab Safety Population; mM = Modified maintenance Primary Population, mS = Modified Safety Population; PT = Preferred Term; S = Safety Population; SAE = serious adverse event; SOC = System Organ Class; TEAE = treatment-emergent adverse event.

Statistical comparisons will be performed using Fisher's exact test. Odds ratio will be provided.

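### Maintenance AE comparisons use percentages, odds ratios and Fisher's test although safety data stop at efficacy-driven escape; the SAP adds no measure based on time at risk

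*SAP*

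**What the plan says.** SAP 6.1.3 covers patients in the maintenance primary and secondary populations, modified or not, who meet the escape criterion. For them, "only data in the Maintenance Blinded Period (up to the time of escape) will be included in both efficacy and safety analyses". Table KGAC.6.1 repeats the rule for the Maintenance Primary Population (MPP) and its modified form (mMPP): "Only information prior to escape will be presented". Under SAP 5.1.3.2, re-randomized patients escape when EASI-50 is not maintained at Week 24, 32, 40 or 48, and then receive open-label lebrikizumab.

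Table KGAC.6.2 names the comparisons: Q2W versus placebo and Q4W versus placebo. For the method, SAP 6.1.3.1 says that Fisher's "exact test will be used for AEs and other categorical safety measures", with odds ratios. SAP 6.14.2 adds: "Summary tables will include the number and percentage of patients reporting an event", and below Table KGAC.6.13: "Odds ratio will be provided". No row of that table is a rate or a time-to-first-event display. The maintenance Kaplan-Meier examples in 6.1.3.1 are all losses of efficacy response.

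Three other statements bear on the point:

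- SAP 6.14.1: "Duration of exposure to study treatment will be summarized by treatment group", with total patient-years.
- SAP 6.7: for the Maintenance Period, "the number and percentage of patients who entered the escape arm will be summarized".
- SAP 6.14.2: the AE summaries are "described more fully in compound level safety standards", a document that is not part of the protocol or SAP.

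**The concern.** A percentage of patients with an event can be compared between arms only if the arms were observed for similar lengths of time. Here observation ends early for patients who lose response, and whether they lose response may depend on the arm. The SAP itself allows for this: Table KGAC.6.12 plans a log-rank comparison of time to loss of EASI-50, the escape criterion, for each active regimen against placebo. The AE tables make no such allowance.

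If placebo patients escape more often or earlier, they have less time in which to report an event. Their percentages are then too low, and the odds ratios shift against lebrikizumab. If active patients escape more, the shift reverses. What is at stake is how the maintenance AE percentages and odds ratios are read.

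**Working it through.** The documents contain no figure to reproduce on this point: no escape rate, AE rate or planned maintenance arm size. The calculation below is an illustration under stated assumptions.

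**Inputs from the documents**
- Maintenance follow-up is 36 weeks (SAP 5.1.3). Escape visits at Weeks 24, 32, 40 and 48 fall 8, 16, 24 and 32 weeks after re-randomization.
- Re-randomization is 2:2:1 (SAP 5.1.3.1).

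**Assumptions**
- The AE hazard is constant and the same in both arms, with a 36-week risk of 10%, 30% or 60%.
- Escapes are spread evenly over the four visits. Other dropout is ignored.
- Arm sizes: 400 × 2/3 = 267 on lebrikizumab in induction. At the Phase 2b EASI-75 rate of 48% (SAP 5.2), 267 × 0.48 = 128 responders, which splits 51:51:26. One placebo patient is then 1/26 = 3.8 percentage points.

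**Formulas**
- Hazard per week: h = −ln(1 − risk)/36.
- Probability of an event by week t: F(t) = 1 − exp(−h·t).
- With escape proportion e, the observed risk is (1 − e)·F(36) + e × the mean of F(8), F(16), F(24), F(32).

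**Worked case: 30% risk, escape 5% (lebrikizumab) versus 20% (placebo)**
- h = 0.3567/36 = 0.00991.
- F = 7.62%, 14.66%, 21.16%, 27.17% at the escape visits (mean 17.65%), and 30.00% at 36 weeks.
- Lebrikizumab: 0.95 × 30.00 + 0.05 × 17.65 = 29.38%.
- Placebo: 0.80 × 30.00 + 0.20 × 17.65 = 27.53%.
- Odds ratio: (29.38/70.62)/(27.53/72.47) = 1.10, although the hazards are equal.

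**All cases** (36-week risks of 10% / 30% / 60%)

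| Escape, lebrikizumab vs placebo | Mean follow-up, weeks | Odds ratio | Gap, points |
|---|---|---|---|
| equal | equal | 1.00 / 1.00 / 1.00 | 0 |
| 5% vs 20% | 35.2 vs 32.8 | 1.08 / 1.10 / 1.14 | 0.7 / 1.9 / 3.3 |
| 10% vs 30% | 34.4 vs 31.2 | 1.11 / 1.13 / 1.19 | 0.9 / 2.5 / 4.3 |
| 10% vs 50% | 34.4 vs 28.0 | 1.25 / 1.29 / 1.42 | 1.7 / 4.9 / 8.7 |
| 20% vs 5% | 32.8 vs 35.2 | 0.93 / 0.91 / 0.88 | −0.7 / −1.9 / −3.3 |

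**Fisher flags.** Exact binomial enumeration with 51 versus 26 patients and two-sided p < 0.05 gives a flag rate of 3.0% to 3.6% with equal escape. It is at most 4.3% at 5% versus 20%, and at most 4.8% at 10% versus 30%. At 10% versus 50% it is 2.6% / 5.1% / 8.5%.

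**Effect of the remedy.** Mean time at risk, ending at first event, escape or Week 52, equals observed risk divided by h. In the worked case this is 29.66 versus 27.79 weeks. Events over time at risk then give 0.2938/29.66 and 0.2753/27.79 per week. Both are 51.7 per 100 patient-years. In every case above the two arms agree, at 15.3, 51.7 and 132.8 per 100 patient-years for the three risks.

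**The case against.** The strongest reply is that the compound-level safety standards may already contain exposure-adjusted rates. SAP 6.14 and 6.14.2 defer to them, and they cannot be checked here. This stands: the point is about what this SAP specifies, and if the standards cover it, one citation is enough.

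Second, patient-years by arm and the number entering escape are reported, so a reader can see unequal follow-up. That is so, but neither is tied to the AE counts, and exposure in 6.14.1 does not end at the first event.

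Third, SAP 6.14 treats safety p-values only as flags. That limits the harm from Fisher's test, but it does not correct the percentages or odds ratios.

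Fourth, the moderate cases are small. At 30% risk the 95% half-width of the crude difference is 1.96 × √(0.3 × 0.7 × (1/51 + 1/26)) = 22 points, against a bias of 1.9 to 2.5 points. This also stands and keeps the priority low. Imprecision and systematic shift are still different problems.

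A reader might infer more than the documents support:

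- *That maintenance AE results will be biased against lebrikizumab.* No escape rates are given, so neither direction nor size is known.
- *That stopping safety data at escape is itself wrong.* Escapees move to open-label lebrikizumab, so ending the randomized comparison there is reasonable.
- *That the special safety topics are affected.* SAP 6.14.6 by default uses the Modified Safety and All Lebrikizumab Modified Safety Populations, not the maintenance arms.

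**Conclusion.** The point holds as a gap in this SAP and is worth a low-cost change. Maintenance AE comparisons between each lebrikizumab regimen and re-randomized placebo are distorted whenever escape, and so time at risk, differs between arms. Under equal constant hazards and evenly spread escape, the spurious odds ratio is about 1.1 to 1.2 for moderate gaps and 1.25 to 1.4 for 10% versus 50%; it is 1.00 with equal escape and reverses if active patients escape more. The escape rates, hazards and arm sizes are assumptions.

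The tables affected are the rows of Table KGAC.6.13 for mMPP, and for MPP the overview and maximum-severity rows. The treatment-emergent laboratory and vital-sign tables for mMPP (Tables KGAC.6.14 and KGAC.6.15) share the same unequal follow-up. The induction comparison is untouched.

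Separately and minor: SAP 6.14.1 excludes maintenance placebo time from exposure for the combined induction and maintenance periods, but states no such exclusion when follow-up is added. This is a difference in definition. A mismatch with the AEs counted is not shown, because 6.1.5 leaves those details to the compound-level standards.

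**What to change.** 1. For the mMPP rows of Table KGAC.6.13 (at least overview, preferred term, SAE and discontinuation), and for the MPP overview, add beside the percentages the number of patients with an event per 100 patient-years at risk. Time at risk ends at first event, escape or end of the blinded period. Give rate differences with 95% CIs. If the compound-level standards already provide this, cite the relevant part in SAP 6.14.2 instead.
2. Footnote the mMPP treatment-emergent laboratory and vital-sign tables to say that follow-up ends at escape and may differ by arm.
3. In SAP 6.14.1, handle maintenance placebo time the same way in both exposure rules, or report it on a separate line.

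The cost is one derivation, time to first event per term, plus extra columns. Intervals will be wide. With e events and T patient-years at risk per arm, the half-width is 1.96 × √(e₁/T₁² + e₂/T₂²) × 100. With 51 versus 26 patients, over the three cases where placebo escapes more, it is about 24 to 25 around a rate of 15, 46 to 49 around 52, and 83 to 87 around 133 per 100 patient-years. Escape reflects worsening disease, so censoring at escape remains informative for AD-related terms. Those rows need caution under either display, and the rates should supplement the percentages, not replace them.

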6.1.3.1. Modified Maintenance Primary and Maintenance Primary Populations

Unless otherwise specified, treatment comparisons of categorical efficacy and health outcomes variables will be analyzed using CMH test with treatment group and covariates as mentioned in Section 6.3 in the model. The CMH p-value will be reported, and the CMH adjusted odds ratio along with the 95% two-sided asymptotic (ie, not continuity corrected) CIs.

Each continuous efficacy and health outcomes measure score, change from baseline and percent improvement from baseline will be summarized by treatment group at all scheduled visits during Maintenance Period including Week 52, using descriptive statistics (n, mean, standard deviation (SD), median, minimum and maximum).

Treatment comparisons for continuous efficacy and health outcome variables will be made using ANCOVA model as specified.

When the ANCOVA is used, the model will include treatment, baseline value and covariates as mentioned in Section 6.3. The ANCOVA analysis will be conducted as described in Section 6.1.2.

The KM product limit method will be used to estimate the survival for time to event analyses (eg, time to loss of IGA response or time to loss of EASI-50 or time to loss of EASI-75). The stratified log-rank test will be performed with treatment group and covariates as mentioned in Section 6.3 in the model. A KM plot of the time to event by treatment group may be provided.

Unless specified otherwise, Fisher's exact test will be used for AEs and other categorical safety measures. Odds ratios will be created with lebrikizumab treatment as the numerator and placebo as the denominator. Continuous vital sign and laboratory values will be analyzed by an ANCOVA model with treatment and baseline value as independent variables.

